**Protocol**

Study Title: Integrative Medicine for Hypermobility Spectrum Disorder (HSD) and Ehlers-Danlos (EDS) syndromes: A mixed-methods feasibility study (IMforHSDandEDS)

PI: [name]

IRB #: DH10320/PRAF

Approval Date: 03.03.21

Version: 3.0

- Participants will also be assessed for any adverse events during check-in calls with the following question, "Are you experiencing any new symptoms or side-effects that you may have noticed?" We will recommend cessation of the food plan if a patient feels that any of their symptoms have been exacerbated, or if they are experiencing any new symptoms.
- Dietary alterations involving increased fats, protein, fruits, and vegetables may cause gastrointestinal distress. HSD and EDS are associated with motility issues that may result in constipation; however, adherence to a Mediterranean-style food pattern has been associated with improved gastrointestinal symptoms. We will monitor these symptoms closely and recommend cessation of the food plan if a patient is experiencing significant digestive distress.

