### **E.4 Participant and Procedure Schedule**

#### **E.4.1 Overview**

The study is comprised of 1 in-person screening, 2 follow-up visits, and 2 telephone or email check-in correspondences for additional support. The in-person screening and 2 virtual follow-up visits will take place at the Healthy Living Community clinic. Virtual follow-up study visits will take place via the Zoom video platform utilized by ChARM TeleHealth, a web-based and HIPAA compliant server maintained by the Healthy Living Community clinic and will occur at 5- and 9-weeks post-enrollment.

During the in-office screening, participants will have their joint mobility measured in accordance with the Brighton Scoring System to confirm that they meet the diagnostic criteria for Hypermobility Spectrum Disorder. Participants who are diagnosed using the Brighton criteria and meet other eligibility criteria will then be asked to provide informed consent (E.4.3) and enrolled in the study if willing. The Clinical Investigator will capture a complete and detailed medical history of enrolled participants, discuss family and social support, as well as prescribe a food plan. The CI will also assess the patient's current self-management strategies and provide general behavioral and psychosocial support. During the 2 follow-up visits, the Clinical Investigator will revisit these self-management strategies. As scheduling visits may be difficult at precisely 5 and 9 weeks, we will leave some flexibility for these points in time to accommodate the schedules of the Clinical investigator, the student researcher, and the participants.

At 2 and 6 weeks, the participants will be contacted by the student researcher to answer any questions, provide nutritional and psychosocial support, monitor for any adverse events, and offer solutions to any dietary challenges. Participants will also be assessed at all study visits for any adverse events.

Participants will be asked to complete pain (VAS), and health-related quality of life (PROMIS-29) instruments at baseline, 5, and 9 weeks. Adherence to the dietary recommendations, as well as the feasibility of food tracking will be obtained using *MyFitnessPal*, a food tracker app throughout the 9 weeks. A food plan satisfaction survey will be collected at 5 and 9 weeks. Participants will fill out the

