#### **E.4.5 Check-in #1 (2 weeks)**

Participants will receive a phone call or e-mail from the student researcher that will answer any questions, provide nutritional and psychosocial support, and offer solutions to any dietary challenges. The goal is to provide support with dietary adherence. This will occur 2 weeks after Visit # 1 and will be set up in advance at a time that works for the participant. If the participant is not available, we will send a check-in email and answer any questions, provide nutritional and psychosocial support, and offer solutions to any dietary challenges by email, if requested. The nutrition counseling script contains suggestions for a general healthy eating pattern but is not a part of food plan adherence. (See Appendix 3B)

Participants will be assessed for any adverse events with the following question, "Are you experiencing any new symptoms or side-effects that you may have noticed?" (See Appendix 3B)

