#### **E.4.7 Check-in #2 (6 weeks)**

Participants will receive a phone call or e-mail from the student researcher that will answer any questions, provide nutritional and psychosocial support, and offer solutions to any dietary challenges. The goal is to provide support with dietary adherence. This will occur 2 weeks after Visit # 2 and will be set up in advance at a time that works for the participant. If the participant is not available, we will send a check-in email and answer any questions, provide nutritional and psychosocial support, and offer solutions to any dietary challenges by email, if requested. The Nutrition counseling script contains suggestions for a general healthy eating pattern but is not a part of food plan adherence. (See Appendix 3B)

Participants will be assessed for any adverse events with the following question, "Are you experiencing any new symptoms or side-effects that you may have noticed?" (See Appendix 3B)

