- A set of measurements that assess joint hypermobility through a 9-point scale will be documented during the in-office screening. For every joint that can be extended past a specified angle, 1 point is added to the patient's Beighton score. A score of 4 or more indicates that generalized joint hypermobility is present.
- The Beighton score will be obtained during the baseline screening.

*NUNM Multi-system Adverse Event questionnaire:*

- A multi-system AE questionnaire will be administered at each visit. As HSD and EDS are associated with a considerable list of comorbidities, we will obtain a baseline measure of the AE questionnaire for each participant so that we have documented any pre-existing conditions. We will check on these conditions throughout the 9 weeks to ensure that symptoms have not worsened, in addition to noting any new occurrences. We will monitor these symptoms closely and recommend cessation of the food plan if a patient feels that any of their symptoms have been exacerbated.

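### The adverse-event question at the two check-ins does not prompt for worsening of existing symptoms, which the plan promises to monitor and act on

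*Combined protocol and SAP*

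**What the plan says.** Section E.6 (NUNM Multi-system Adverse Event questionnaire) sets up two ways of collecting adverse events.

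- **Visits.** "A multi-system AE questionnaire will be administered at each visit". A baseline administration records pre-existing conditions, and the plan then commits to follow them: "We will check on these conditions throughout the 9 weeks to ensure that symptoms have not worsened, in addition to noting any new occurrences". Worsening and new events are named as two separate things to look for.
- **Check-ins.** Here the assessment is a single scripted item, put to the participant by phone or e-mail: "Are you experiencing any new symptoms or side-effects that you may have noticed". The same bullet goes on to the action: "We will recommend cessation of the food plan if a patient feels that any of their symptoms have been exacerbated", with new symptoms as a further trigger.

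Sections E.4.5 and E.4.7 repeat the question for the two check-ins, each introduced by "Participants will be assessed for any adverse events with the following question". Both refer to Appendix 3B for the script, which is not in the text available for this review. Both also allow the check-in to be done by e-mail.

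The timing of the second check-in is stated in two ways. Section E.4.1 says "At 2 and 6 weeks, the participants will be contacted by the student researcher to answer any questions", and the heading of E.4.7 agrees with week 6. The body of E.4.7 says "This will occur 2 weeks after Visit # 2", and Visit 2 is the week-5 visit.

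**The concern.** The action rule attached to the check-ins has two limbs, new symptoms and exacerbated ones. The question that feeds it openly prompts only for new symptoms or side-effects. A participant whose long-standing constipation has become worse on the diet can truthfully answer no, unless they already blame the diet and call the change a side-effect. The present tense adds a second gap: a symptom that flared and settled since the last contact need not be mentioned.

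This matters more here than in most dietary studies. Section C.2 lists constipation, gastroparesis and other motility disorders among the features of these conditions. Section E.6 notes how many comorbidities participants bring with them, and names gastrointestinal distress as the risk of the food plan. Aggravation of a symptom already present is thus a harm that the plan itself foresees. If it is not asked about, it may be noticed later than it could be, and the tolerability summary may look somewhat better than it should.

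**Working it through.** No sample size, power or error rate is involved, and the plan gives no figure to reproduce. The check has two parts.

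**1. Commitment against question**

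| Event type | Promised to be followed (E.6) | Tied to action in the check-in bullet (E.6) | Prompted by the check-in question (E.4.5, E.4.7, E.6) |
|---|---|---|---|
| New symptom, present now | Yes | Yes | Yes |
| Existing symptom, worse now | Yes | Yes | Only if the participant regards it as a side-effect |
| New or worse since last contact, now settled | Not addressed separately | Not addressed separately | No, by the tense of the question |

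The second row is the mismatch. It lies within a single bullet of E.6, so it does not depend on how one reads the wider promise to monitor.

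**2. What it does to timing**

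Inputs:
- Visits with the multi-system questionnaire: baseline, week 5, week 9 (E.4.4, E.4.6, E.4.8).
- Check-ins with the single question: week 2 and week 6 (E.4.1), or week 2 and week 5 + 2 = 7 (body of E.4.7).
- Start of the food plan: after a 1-week lead-in (E.4.4), so at about week 1.

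Of the four post-baseline contacts, two (weeks 5 and 9) use the instrument that has a baseline reference and two use only the single question.

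Time on the food plan before the first systematic check for worsening:
- As written: 5 − 1 = 4 weeks.
- If the check-in question also asked about worsening: 2 − 1 = 1 week.

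Intervals on the food plan between systematic checks for worsening:
- As written: weeks 1 to 5 and 5 to 9, so 4 and 4 weeks; longest 4.
- Reworded, second check-in at week 6: 2 − 1 = 1, 5 − 2 = 3, 6 − 5 = 1, 9 − 6 = 3; longest 3.
- Reworded, second check-in at week 7: 1, 3, 7 − 5 = 2, 9 − 7 = 2; longest 3.

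The main gain is the earlier first check, 1 week against 4. The longest gap shortens only from 4 weeks to 3, whichever date for the second check-in is meant. All of these are approximate, because E.4.1 allows the visits some flexibility around weeks 5 and 9.

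**The case against.** There is a fair case on the other side.

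- **The question includes side-effects.** In a conversation about the diet, that word may well draw out a gut symptom that has become worse. This stands as a limit: one cannot say that the check-ins are unable to detect worsening. But the route works only once the participant has made the causal link, and finding worsening should not depend on that.
- **The promise may be met by the visits.** The sentence about worsening sits in the bullet on the visit questionnaire, so the whole of the 9 weeks might mean baseline, week 5 and week 9, with the check-in question as a supplement. That reading is possible. It does not remove the mismatch in the check-in bullet, where exacerbation triggers action but is not asked about.
- **There are other routes.** E.4.1 gives the check-ins a general remit to watch for adverse events, participants can raise difficulties in discussion, and the satisfaction survey covers physical side-effects (B.2) and negative outcomes (E.6). These can catch worsening. However, discussion is unprompted on this point, and E.6 places the survey at weeks 5 and 9, so it does not bring the first check forward.
- **Appendix 3B may hold further prompts.** It may; it was not available. But E.4.5, E.4.7 and E.6 each present this one question as the adverse-event assessment, so the protocol text needs aligning in any event.
- **Little rests on it analytically.** Correct. No aim has an adverse-event endpoint, and recruitment and retention are untouched.

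**Conclusion.** The point holds as a modest defect in safety ascertainment. The check-in question does not prompt for worsening of existing symptoms, although the plan promises to follow worsening and ties action to it. The first systematic check therefore comes about 4 weeks into the food plan when it could come at about 1 week. Worsening that persists should be found at week 5 or 9, on the assumption that the multi-system questionnaire, whose text was not available, captures it against baseline as E.6 implies. What may be missed is mainly worsening that resolves between contacts. The resulting under-count is possible but of unknown size.

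A reader might go further, and the documents do not support it:

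- **That worsening is the likeliest adverse event.** No section says so. E.6 and E.8 name gastrointestinal effects that could equally be new, and E.6 also cites improved gastrointestinal symptoms with this eating pattern.
- **That the reported count will be too low.** This is a risk, not an established result, given the other routes.
- **That a given number of participants is affected.** The documents give no prevalence of baseline gut symptoms. If one assumed 30% to 70% of 20, that would be 0.30 × 20 = 6 to 0.70 × 20 = 14 people. They would be people with a symptom that could worsen, not people who worsen or whose worsening is missed.

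**What to change.** Reword the question in E.4.5, E.4.7 and E.6, and align Appendix 3B, so that it covers new and worsened symptoms over the whole interval. For example: *Since our last contact, have you had any new symptom, or has any symptom you already had become worse, even if it has since settled?* Use the same sentence by phone and by e-mail. Record new and worsened events separately, with worsening judged against the baseline questionnaire.

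The cost is one sentence in the protocol and the script, slightly longer calls, and possibly a higher reported adverse-event count.

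Two related inconsistencies should be reconciled by the study team in the same edit. The date of the second check-in differs between E.4.1 and the body of E.4.7. The circumstances in which cessation of the food plan is advised are also worded differently across the bullets of E.6 and in E.8: exacerbation alone, exacerbation or new symptoms, or significant digestive distress. No action rule is proposed here.

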## E.7 Data Collection and Sources

### E.7.1 Confidentiality and Data Storage

There is a very small risk that information about a study participant could be inadvertently disclosed to non-study personnel. Throughout the study, measures to ensure the privacy of information on study subjects will be maintained. All study investigators and staff have been certified in the use of human subjects in research and have received training in HIPAA regulations. Participants and staff will be informed of the confidentiality of information and assured that data will be used only for statistical purposes and group analyses in which the individual cannot be identified. No data beyond what is stated in the informed consent will be sought without authorization from the participant. Information on illnesses and hospitalizations will not be sought from hospitals or doctors without a signed medical release from the subject. Conversely, no information on any individual will be released to anyone other than study personnel without a signed medical release from the participant, or where appropriate, the next of kin or a physician in case of a life-threatening emergency to the subject. All study personnel will be instructed not to discuss any participants with persons other than study personnel.

Each participant will be assigned a unique alpha-numeric ID upon screening. All data resulting from study visits will be collected on standardized case report forms (CRFs). Data will be transferred from CRFs to a secure REDCap database for data management. Outcome data from *MyFitnessPal* will be entered into the REDCap database by the student researcher. Data will be downloaded only onto a password protected computer; upon download, data will be immediately entered into REDCap and deleted from the hard drive. Food VAS, Patient Assessment of Chronic Illness Care (PACIC+), and PROMIS-29 surveys will all be recorded utilizing the REDCap database. REDCap is a secure, web-based application that supports electronic data capture for research studies. REDCap features include: 1) intuitive data entry features; 2) audit trails for tracking data manipulation and export; 3) user-based privileges that support HIPAA compliance; 4) seamless data export to common statistical packages; and 5) procedures for importing data from external sources. The REDCap database will be accessible only by the study team. The link between study IDs and protected health information will be kept as a single electronic file stored on a limited-access electronic folder on a secure server with select access limited to the study team. Data will be destroyed 3 years after completion of the study. Computer files will be deleted from the server, and paper files will be destroyed using a professional document shredding service.

### Protocol

Study Title: Integrative Medicine for Hypermobility Spectrum Disorder (HSD) and Ehlers-Danlos (EDS) syndromes: A mixed-methods feasibility study (IMforHSDandEDS)

PI: [name]

IRB #: DH10320/PRAF

Approval Date: 03.03.21

Version: 3.0

All completed forms will be kept in locked files to which only project personnel have access. These files will also be in locked rooms. Data from paper forms will be manually entered into REDCap and kept as electronic files. Paper forms will continue to be stored in a locked cabinet up to completion of data analysis, at which point they will be shredded. Electronic files will be password protected with access given to study personnel only. All analyses will be conducted by study staff at the Helfgott Research Institute. The study statistician will only access de-identified data exported from REDCap. Only de-identified data will be presented in any reports, presentations, or manuscripts.

While the safety of integrative medicine is dependent on individual therapies or treatments, mind-body practices and light movement exercises are generally considered to be safe. The Clinical Investigator will evaluate the participant’s current supplements and medications before making food plan recommendations to prevent any drug interactions that could occur.

### **Protocol**

Study Title: Integrative Medicine for Hypermobility Spectrum Disorder (HSD) and Ehlers-Danlos (EDS) syndromes: A mixed-methods feasibility study (IMforHSDandEDS)

PI: [name]

IRB #: DH10320/PRAF

Approval Date: 03.03.21

Version: 3.0

Participants enrolled in the 9-week integrative medicine intervention will receive 3 complimentary office visits and 2 check-in calls from the student researcher. There may be little direct benefits to the participants other than the personal satisfaction of contributing to health research; however, if they respond positively to integrative care, and it was effective in reducing pain and improving quality of life among patients, it is possible that some of the symptoms associated with the disorder could show some relief.

### **E.9 Statistical Analysis**

All measures collected in the study, including baseline characteristics and outcome measures, will be summarized using mean and SD (biomarkers, anthropometrics), median and IQR (Beighton score), or percentage within each level, for categorical variables. All statistical analyses will be performed at the National University of Natural Medicine.

For Specific Aim 1,

Feasibility of the 9-week integrative medicine intervention will be measured through recruitment and retention at each follow-up visit. Recruitment rate will be presented as the mean number of participants enrolled per month, with enrolment ceasing either after 4 months, or when n=20 participants have been enrolled. Retention will be calculated as the percentage of enrolled participants from whom follow-up data is obtained, at either the 5-week or 9-week visit.

For Specific Aim 2,

Adherence to the recommended diet will be assessed in different ways and tracked by macronutrient levels and dietary composition. In particular, we will assess:

- Percentage of days on which the diet recommendations were met; in order to satisfy this requirement, macronutrient distribution must meet all of the following:
  - Carbohydrates between 40-50%
  - Protein between 15-20%
  - Fat between 25-30 %
- Number of weeks in which recommendations were met at least 5 days;
- Whether recommendations were met on at least 75% of total days (Y/N)
- Mean of weekly adherence scores calculated over the 9-week study period.

Percentage of days and weeks adherent will be summarized across participants as median/IQR/range. We will also present the percentage of participants who met the threshold of 75% days adherent.

Feasibility of the 9-week integrative medicine intervention will also be measured through self-reported food plan satisfaction surveys that assess any negative outcomes, overall cost-prohibitiveness or

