### **E.3.2 Exclusion Criteria**

- Pregnant and lactating women, or planned pregnancy over the next 3 months
- Consumption of more than 14 (men) or 7 (women) alcoholic drinks per week
- History of disordered eating or eating disorder
- Body mass index (BMI) considered underweight (<18.5)
- Weight loss from metastatic cancer
- Unable to make dietary changes or participate in a 9-integrative medicine nutritional intervention
- Those with significant dietary changes, new medications, or new exercise routines within the past 90 days
- Currently, or already, a patient of [name] and Healthy Living Community

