#### MyFitnessPal

#### **Protocol**

Study Title: Integrative Medicine for Hypermobility Spectrum Disorder (HSD) and Ehlers-Danlos (EDS) syndromes: A mixed-methods feasibility study (IMforHSDandEDS)

PI: [name]

IRB #: DH10320/PRAF

Approval Date: 03.03.21

Version: 3.0

*MyFitnessPal*, a food tracker available on both Apple and Android for mobile devices, as well as both Windows and Mac computer platforms, will be used to collect estimated daily dietary intake for participants. *MyFitnessPal* has a database of nutritional information for over 11 million foods that will allow participants to capture their general diet by manually adding individual ingredients, barcode scanning, or finding whole meals. In a comparison of micronutrients and calories between diet-tracking apps and the USDA database, *MyFitnessPal* was shown to have the best coding accuracy. Self-reported data, however, may be subject to inaccuracies. When foods are entered into the *Diary* feature located in the app, the *Nutrient Dashboard* displays daily calories, as well as macronutrient proportions, broken down into carbohydrates, fats, and protein.

Participants will be encouraged to track their daily diet to the best of their ability, and for weeks that there is missing data, a threshold of no less than 3 days of tracking (including breakfast, lunch, dinner, and snacks) per week for the 9-week study duration will be considered adherent and averaged appropriately. Individuals with previous disordered eating patterns, or discomfort with food tracking, will be able to opt-out; however, they will still be shown how to use *MyFitnessPal* to analyze dietary composition for adherence. A 1-week lead-in prior to introducing the food plan will be utilized to provide a baseline record of the participant's general diet. *MyFitnessPal* data will allow us to track general adherence to dietary changes, the overall quality of the participant's diet, and average macronutrient proportions. By measuring the participant's reported macronutrient percentage scores and comparing them with the prescribed food plan, we will be able to calculate an adherence score.

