### Secondary Outcome measures:

#### *Dietary Adherence/Food Tracking Feasibility (MyFitnessPal food tracking):*

- Dietary adherence will be measured by self-reported food tracking through Daily Nutrition Goals in the *MyFitnessPal* app and will be documented at 5 and 9 weeks through the Friends feature. Daily macronutrient contributions will be obtained as percentages of total intake. The suggested macronutrient breakdown for the food plan is 40-50% calories from a carbohydrate source, 35-40 % calories from fat, and 15-20% calories from protein. Weekly recorded consumption of the participant will be compared to this standard for an adherence score. For each of the three macronutrient categories, we will give 2 points if the percentage is within the required range and 1 point if the percentage is within 5% of the required range (maximum 6 points total). A score of 4 and above will be considered adherent to the food plan.
- The feasibility of food tracking will be measured by adherence to the recommended use of the app. A threshold of 3 days of reporting per week (including breakfast, lunch, dinner, and snacks) for the 9-week duration of the study will be considered adherent and should provide sufficient data to assess the observance of the recommended food tracking.

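### The E.9 daily diet-adherence rule requires 25-30% fat while participants are prescribed 35-40%, so every day inside the prescribed fat range is scored as non-adherent

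*Combined protocol and SAP*

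**What the plan says.** The target given to participants is the same in E.4.4 (Visit 1) and E.5 (Intervention): 40-50% carbohydrate, 15-20% protein, 35-40% fat. E.6 scores each week against that standard, including "35-40 % calories from fat, and 15-20% calories from protein". It gives 2 points per macronutrient in range and 1 point if within 5%, to a maximum of 6, and states: "A score of 4 and above will be considered adherent to the food plan".

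E.9, under Specific Aim 2, adds a daily rule: "in order to satisfy this requirement, macronutrient distribution must meet all of the following". The carbohydrate and protein ranges listed there match the prescription, but the third line is "Fat between 25-30" percent. Three summaries rest on this rule:
- the percentage of days on which the recommendations were met;
- the number of weeks with at least 5 such days;
- a yes/no indicator for at least 75% of days, also reported as a percentage of participants.

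The fourth summary is the mean weekly score from E.6. E.8 (Risks and Benefits) also describes the recommended plan as 25-30% fat.

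**The concern.** A rule meant to record whether the recommendations were followed uses a fat range that nobody is asked to follow. With 25-30% fat, a participant who does exactly what was prescribed is recorded as never adherent. The lower fat range also fits poorly with the other two ranges: if the three shares make up the whole of intake, almost no diet can satisfy all three at once.

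Adherence to the food plan is half of the secondary aim (B.2), and section F says the methods could be carried into a larger study. Followed as written, the analysis could report a diet that participants kept to as infeasible, next to a weekly score that says the opposite on the same data.

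**Working it through.** The plan has no calculated figure to reproduce here; the check is whether the ranges agree with each other.

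**Inputs.** Carbohydrate 40-50 and protein 15-20 (identical in E.4.4, E.5, E.6, E.8 and E.9). Fat 35-40 (E.4.4, E.5, E.6) or 25-30 (E.8, E.9). Weekly scoring rule from E.6. On the scale of the shares, E.5 says the app "displays daily calories, as well as macronutrient proportions, broken down into carbohydrates, fats, and protein", a three-way split, while E.6 says "Daily macronutrient contributions will be obtained as percentages of total intake".

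**Step 1, overlap.** The top of the E.9 fat range is 30 and the bottom of the prescribed range is 35, a gap of 35 - 30 = 5 points. No day with fat of 35-40% can pass E.9. This needs no assumption about sums, rounding or alcohol.

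**Step 2, joint feasibility if the shares sum to 100.**
- E.9 ranges: lower limits 40 + 15 + 25 = 80, upper limits 50 + 20 + 30 = 100. A total of 100 is reached only with every share at its upper limit, that is at 50/20/30 (carbohydrate/protein/fat).
- Prescribed ranges: 40 + 15 + 35 = 90 to 50 + 20 + 40 = 110. A total of 100 lies well inside.

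**Step 3, sensitivity to the sum.** Whole-percent compositions meeting all three ranges:

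| Total of the three shares | E.9 (fat 25-30) | Prescribed (fat 35-40) |
|---|---|---|
| 100 | 1 | 36 |
| 99 to 101 (separate rounding) | 4 | 106 |
| 95 (assumed 5% of energy from alcohol) | 21 | 21 |
| 90 (assumed 10% of energy from alcohol) | 36 | 1 |

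Alcohol matters because the exclusion in E.3.2, "Consumption of more than 14 (men) or 7 (women) alcoholic drinks per week", permits some drinking; the 5% and 10% shares are assumptions. In no row does a composition passing E.9 have fat of 35-40%.

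**Step 4, daily rule against weekly score** (reading within 5% as 5 percentage points).
- 45/17.5/37.5 every day: weekly score 2 + 2 + 2 = 6 of 6; under E.9, 0% of days, 0 weeks, No at 75%.
- 50/20/30 every day: passes E.9; weekly score 2 + 2 + 1 = 5 of 6, because fat is 5 points below 35.
- Of the whole-percent compositions summing to 100, 206 score 4 or more and so count as adherent under E.6. Exactly 1 of them, 50/20/30, meets E.9.

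If within 5% is read as relative to the range limits, 102 compositions score 4 or more and 50/20/30 scores 4 (fat of 30 is below 0.95 × 35 = 33.25). Still only that one meets E.9.

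**Step 5, after correction.** With fat at 35-40% in E.9, all 36 whole-percent compositions that pass (sum 100) score 6 of 6 on the weekly score, so the two measures agree on them.

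**The case against.** The strongest reply concerns weight. B.2 declares the diet-adherence outcome as a score comparing intake with the prescribed plan. E.6 defines that score with 35-40% fat and supplies the only cut-off for being adherent to the plan. E.9 keeps it. The daily rule appears only in E.9, its summaries are descriptive, no test or sample size depends on them, and the study enrols at most 20 people. Daily percentages are collected, so everything can be rescored. An analyst could also take 35-40% from E.4.4, E.5 and E.6 without looking at results.

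Most of this stands. The weekly score, the tracking measures, the satisfaction surveys and the primary aim of recruitment and retention are untouched, and the error is recoverable. It does not follow that the correction can wait. E.8 repeats 25-30%, so the text does not settle the range by itself, and an undocumented choice made at analysis could not be told apart from one made after seeing the data.

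It is also fair that the single-composition result depends on the shares summing to 100, and that it weakens if alcohol is in the denominator. The non-overlap of the fat ranges does not depend on this and is enough to establish the fault. The appendix food plans handed to participants were not available for this check, so what they are told is taken from the protocol text.

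**Conclusion.** The concern holds. Applied as written, three of the four E.9 diet-adherence summaries are zero or No for a participant who keeps fat within the prescribed 35-40%, whatever the treatment of rounding or alcohol. If the shares sum to 100, one whole-percent composition satisfies E.9, against 36 under the prescribed ranges. The count of 206 weekly-adherent compositions rests on the percentage-point reading of the E.6 tolerance; the finding that only one of them meets E.9 does not.

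The text points to 35-40% as the intended range: it is the figure in both descriptions of what participants receive and in the weekly score, and it is compatible with the other two ranges at a total of 100. Aim 2 is compromised but not unanswerable. The correction must be made before analysis because a pre-set 75% criterion is wrong as it stands.

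**What to change.** Before analysis, change the fat range to 35-40% in E.9 and E.8. State whether alcohol energy is in the denominator and how the shares are rounded before they are compared with the limits. The cost is protocol and SAP wording only; the daily percentages are already collected.

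If the clinical team really intends 25-30% fat, then E.4.4, E.5 and E.6 are wrong instead. Those sections and the participant instructions would have to change, and the carbohydrate or protein range would have to be widened so that the three can total 100 at more than one point.

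One limit of the correction: requiring all three ranges every day stays strict. As an illustration, take independent normal day-to-day variation in carbohydrate and protein around 45/17.5/37.5, with fat as the remainder. Assumed SDs (carbohydrate/protein) of 1/0.5, 2/1, 4/2 and 6/3 points give about 97%, 73%, 35% and 19% of days passing the corrected rule. A participant on target on average could therefore still miss the 75% criterion, and a low result should be read alongside the weekly score.
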